9.1.5 Secondary Efficacy Analysis

The Kaplan-Meier survival curve of revision or removal of any component will be displayed at the end of the study using SAS/PROC LIFETEST. Two survival curves will be displayed, one for prospectively enrolled cases only, one for both prospectively enrolled cases and retrospectively enrolled cases. And the 10-year survival rate and 95% Confidence Interval will be presented as well.

For the Additional Data Collection when data is available, descriptive statistics (e.g., mean, percentage) and 95% confidence interval will be presented.

The descriptive statistics (e.g., mean, minimum, maximum, standard deviation) of length of OR time, hospital stay, and amount of blood loss will be presented.

A change of the KSS scores, ROM, LEAS, KOOS, Activity Questionnaire activity levels, and SF-12 scores at each post-surgery visit from pre-surgery will be summarized. The descriptive statistics (e.g., mean, standard deviation) will be presented, where applicable. In addition, a p-value will be presented to determine of the change from pre-surgery is non-zero, if appropriate.

Radiographic data will be summarized in table format.

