Appendix A Component Listing

Appendix B FDA 510K Clearance Letters

Appendix C Product Labeling

Appendix D Model Informed Consent Form

Appendix E Sample Case Report Forms

Appendix F Patient Retention Program

List of Abbreviations

AE Adverse Event
AP Anteroposterior
AVN Avascular Necrosis
BMI Body Mass Index

CAD Computer Assisted Design
CSM Clinical Study Manager
DCF Data Clarification Form
EDC Electronic Data Capture
FEA Finite Element Analysis
GCP Good Clinical Practice

HIPAA Health Insurance Portability and Accountability Act

KSS Knee Society Score

KOOS Knee and Osteoarthritis Outcome Score

M/L Medio/Lateral
ML Mediolateral
OA Osteoarthritis

PCL Posterior Cruciate Ligament PER Product Experience Report

PI Primary Investigator
QOL Quality of Life
ROM Range of Motion
SC Study Coordinator
SF-12 Short-Form 12
TA Traumatic Arthritis

UHMWPE Ultra High Molecular Weight Polyethylene UKA Unicompartmental Knee Arthroplasty

Study Synopsis

Title	The Triathlon [®] PKR Unicondylar Knee System Outcomes Study
Short Title	Triathlon [®] PKR Study
Protocol Number	66
Phase	Post-marketing
Methodology	This study is a prospective, post-market, multi-center evaluation of the Triathlon [®] PKR unicondylar knee system with an additional retrospective enrolled and prospectively followed cohort of cases.
Study Duration	10-year follow-up for each case
Study Center(s)	A minimum of four centers will participate.
Objectives	Primary: The 10-year mean KSS Function Score is comparable to the Triathlon CR KSS Function Score at 10-years. Secondary: A 10-year Kaplan Meier survival analysis will be presented including only prospective cases.
Additional Data Collection	To compare OR time, hospital stay, blood loss, return to ROM, KSS, activity level, adverse event rates, and radiographic data to UKA.
Reference Therapy	Triathlon CR Stryker Sponsored Study; Clinical Trials NCT 00966979; Survivorship data from national registries will supplement the study survivorship data.
Number of Subjects	A total of 175 cases (knees) will be enrolled. There are 80 cases enrolled from the prospective cohort and a planned minimum 95 cases is the goal from the retrospective cohort.

Inclusion Criteria

- 1) The subject is a male or non-pregnant female 21-75 years of age at the time of enrollment.
- 2) The subject requires a primary cemented unicompartmental knee replacement.
- 3) The subject has a diagnosis of osteoarthritis (OA) or post-traumatic arthritis (TA).

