2.1.2 Secondary

A 10-year Kaplan Meier survival analysis will be presented at the end of the study using only the prospective cases, to prevent bias. Survivorship data from the national registries below will be presented along with the study survivorship data.

- Australian Orthopaedic Association National Joint Replacement Registry
- National Joint Registry for England, Wales, Northern Ireland and the Isle of Man
- The New Zealand Joint Registry
- Swedish Knee Arthroplasty Register

Other Data Collected

Surgical Details

The Surgical Details form will record information related to the surgery, such as: duration of surgery, estimated blood loss, and if an intraoperative complication has occurred. Please See Appendix II for a sample Surgical Details Form.

Clinical Outcome

Clinical Outcomes will be evaluated via the total Knee Society Score, including pain and function, pre-operatively, and at the 2-week, 6-week, 3-month, 1, 2, 5, 7- and 10-year visits.

Patient Outcomes

SF-12: General health and well-being will be collected via the SF-12 form at all preoperative and postoperative intervals.

Activity Scales: Three activity assessments will be conducted at each visit. First, the patient will complete the Lower Extremity Activity Scale (LEAS). This questionnaire asks the patient to select one of the options that best describes their physical function at that point in time. The second Activity Questionnaire consists of open-ended entries where the patient can note the recreational/sport activities they are participating in at that point in time. The third questionnaire for the patient to complete is the Knee and Osteoarthritis Outcome Score (KOOS): This score was developed as an instrument to assess the patient's opinion about their knee and associated problems

Radiographic Outcomes

Radiographs will be optional in this retrospective arm of the study. If taken at the annual visit, an anteroposterior, medial-lateral, and merchant or skyline view will be collected.

Although preoperative AP long-standing film will not be collected, it is required to ensure that the patient did not have a deformity of more than 15 degrees of varus/valgus preoperatively during the screening process.

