7.1 Initial Retrospective Evaluation

Once the subject has been screened and confirmed that they meet all inclusion and exclusion criteria, the subject will be consented. A medical record review will commence to obtain baseline information. The subject will be scheduled for the next annual follow-up that they are due for based on the original surgery date and as per the Evaluation Schedule on page 4. The earliest visit accepted will be five years postoperative, which means subjects will have to have a surgery date of 2015 or earlier. The initial medical record review will include obtaining: demographic/medical history, surgical details, a baseline evaluation at either two weeks, six weeks or three months and Knee Society Score elements; pain level and range of motion values. The anteroposterior (AP, standard and long-standing), mediolateral and merchant/skyline x-rays are optional. The AP long-standing film will only be used as a reference to determine if the subject meets the protocol inclusion of not having a preoperative varus or valgus deformity of greater than 15 degrees.

For the initial retrospective cases, as much of the preoperative data and baseline data will be retrospectively collected from the medical records upon completion of written consent. The patient reported outcomes (SF-12, LEAS, Activity Questionnaire and KOOS) will not be available prior to consent but will be collected from the point of consent forward to ten years.

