10.1 Subject Recruitment and Screening

Patients will be recruited at the study sites by a review of medical records for prior cases receiving the Triathlon PKR unicompartmental device. Once a patient is identified as having a PKR unicompartmental device implanted outside of the initial prospective study, it will be determined if they are deceased or had the device revised, which would exclude them during the screening process. Once a patient is identified as a potential study candidate, the study coordinator will review all the inclusion and exclusion criteria to ensure the patient meets those criteria. If that screening is successful, the study coordinator will contact the patient to conduct a telephone screening to review the study details and inquire as to the level of interest to participate. If there is interest, it will be determined if the patient has the capacity to give informed consent, and if so, a verbal informed consent will be provided. A signature will be obtained on the formal approved informed consent document to complete the enrollment into study.

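### The pooled 10-year Kaplan-Meier curve in section 9.1.5 counts event-free time that screening guarantees, so it overstates survival

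*Combined protocol and SAP*

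**What the plan says.** Section 9.1.2 defines the secondary endpoint as revision or removal of any component. Section 9.1.5 sets the method: "The Kaplan-Meier survival curve of revision or removal of any component will be displayed at the end of the study using SAS/PROC LIFETEST". It then calls for a prospective-only and a pooled curve: "Two survival curves will be displayed, one for prospectively enrolled cases only, one for both prospectively enrolled cases and retrospectively enrolled cases". It continues: "And the 10-year survival rate and 95% Confidence Interval will be presented as well". It does not say which curve the rate and interval belong to, and it mentions no entry time, left truncation or caveat for the pooled curve.

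The objectives are narrower. Section 2.1.2 reads: "A 10-year Kaplan Meier survival analysis will be presented at the end of the study using only the prospective cases, to prevent bias". The Study Synopsis agrees: "A 10-year Kaplan Meier survival analysis will be presented including only prospective cases". Section 2.1.2 also sets registry results beside the study's: "Survivorship data from the national registries below will be presented along with the study survivorship data".

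On screening of the retrospective cohort, section 10.1 says of patients found with the device that "it will be determined if they are deceased or had the device revised, which would exclude them during the screening process". On timing, section 7.1 says: "The earliest visit accepted will be five years postoperative, which means subjects will have to have a surgery date of 2015 or earlier". The footnote to the Evaluation Schedule instead makes 2015 the earliest surgical date. Section 3.3 gives 80 prospective and at least 95 retrospective knees, and also admits cases done after the original enrollment goal was met.

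**The concern.** A retrospective knee is in the study only because it had not been revised when it was screened. Its time from surgery to enrollment is event-free by selection, and knees that failed in that window never appear. A Kaplan-Meier estimate that starts every knee at surgery puts this time into the early risk sets, enlarging the denominators while no retrospective events can occur. This is left truncation ignored, and it raises the curve.

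The pooled curve would therefore tend to flatter the device for a reason unrelated to its performance, with no note to tell the reader so. Section 2.1.2 gives prevention of bias as its reason for using prospective cases only, and 9.1.5 then adds the display which that objective excludes. If the 10-year rate and interval were also taken from the pooled curve, they would be too high.

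**Working it through.** **The plan's own figures.** The plan states no expected survival rate, event count or survival sample size, so there is no survival figure to reproduce. Its one sample-size figure, for KSS Function in section 9.4.1, does reproduce: (21 × 2.486 / 6)² = 75.7, rounded up to 76, and 76 / 0.80 = 95. This point does not affect it.

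**Inputs from the documents.** 80 prospective and 95 retrospective knees (section 3.3); no revision before entry in the retrospective cohort (section 10.1); Kaplan-Meier in PROC LIFETEST with no entry time (section 9.1.5).

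**Entry time a, in years after surgery.** With surgery in 2015 or earlier (section 7.1), a protocol version dated September 2019 and about six months of enrollment (section 3.4), a is about 4 or more. The footnote's literal wording, with section 3.3, would allow shorter times, so years 2 and 3 are included. Year 7 arises only under section 7.1.

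**Assumptions not in the documents.** The same hazard in both cohorts; true 10-year survival of 80%, 88% or 95%; constant hazard unless stated; no dropout in the closed form.

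**Closed form.** Up to year a, only the 80 prospective knees can fail while all 175 are counted. After year a, all share the same hazard. So:

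pooled S(10) = [(80 × S(a) + 95) / 175] × S(10) / S(a)

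For true 80% and a = 5: S(5) = 0.8944; (80 × 0.8944 + 95) / 175 = 0.9517; 0.80 / 0.8944 = 0.8944; product 0.851.

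| True S(10) | a = 2 | a = 3 | a = 4 | a = 5 | a = 7 |
|---|---|---|---|---|---|
| 80% | 82.0% | 83.0% | 84.1% | 85.1% | 87.3% |
| 88% | 89.2% | 89.9% | 90.5% | 91.2% | 92.5% |
| 95% | 95.5% | 95.8% | 96.1% | 96.3% | 96.9% |

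With Weibull shapes from 0.7 to 1.5 over the same entry years, true 80% reads 80.9% to 88.2%, true 88% reads 88.5% to 93.0%, and true 95% reads 95.2% to 97.1%.

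**Simulation.** 5,000 trials per scenario, constant hazard, 20% dropout over 10 years, Greenwood variance. The mean pooled estimate agrees with the closed form (for example 0.853 at true 80%, a = 5). The table gives the share of trials in which the whole 95% interval lies above the truth; the nominal share is 2.5%.

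| True S(10), limits | a = 2 | 3 | 4 | 5 | 7 | Prospective-only |
|---|---|---|---|---|---|---|
| 80%, log-log | 8% | 13% | 22% | 36% | 70% | about 1% |
| 80%, linear | 13% | 21% | 33% | 49% | 80% | about 5% |
| 88%, log-log | 5% | 8% | 13% | 21% | 42% | about 1% |
| 88%, linear | 11% | 16% | 25% | 36% | 61% | about 6% |
| 95%, log-log | 2% | 3% | 4% | 5% | 11% | 0% |
| 95%, linear | 13% | 16% | 22% | 27% | 43% | 9 to 10% |

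**With delayed entry.** When retrospective knees join the risk set only at entry, the mean pooled estimate is 0.799 to 0.801 at true 0.80, 0.879 to 0.881 at 0.88, and 0.950 to 0.951 at 0.95.

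**The case against.** - **It is one supplementary display.** The objective is prospective-only and that curve is shown too, so the reader sees an unaffected estimate. This stands, and it limits the severity.
- **The pooled curve need not lie above the prospective one.** This also stands. If the retrospective hazard were twice the prospective one, with entry at year 5 and prospective survival of 80%, the pooled estimate would be (80 × 0.80 + 95 × 0.64 / 0.80) / 175 = 0.80, no higher than prospective-only. But it would still overstate the pooled knees' own survival, which at 80:95 weights is (80 × 0.80 + 95 × 0.64) / 175 = 0.713 if the doubled hazard applies from surgery.
- **Delayed entry is not ruled out.** True. The point rests on silence plus the named procedure, which is reason enough for the plan to state it.
- **A single-component exchange before enrollment might pass the screen.** Section 10.1 speaks of the device being revised, while the endpoint covers any component. Exclusion is the natural reading, but it is an inference.
- **The range is not a bound.** A case may enroll with only its 10-year visit left. Entry at year 9 gives 89.7% at true 80%, so late entry makes the bias larger. Section 9.4.3's per-protocol exclusions would also change the 80 and 95 somewhat.
- **Part of the linear-interval excess comes from the interval type.** Correct, as the prospective-only column shows. At true 95% with log-log limits and entry at years 2 to 4, the share is close to nominal.

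**Conclusion.** The concern holds. Followed as written, section 9.1.5 yields a pooled curve that overstates 10-year survival whenever there is any revision risk before entry, and it conflicts with section 2.1.2 and the Synopsis. With a constant hazard common to both cohorts and entry at years 2 to 7, the excess is 2.0 to 7.3 points at true 80%, 1.2 to 4.5 points at true 88%, and 0.5 to 1.9 points at true 95%. The size depends on the assumed hazard shape and entry times. The direction is the same under either wording of the surgery-year rule.

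The primary endpoint, the prospective-only survival objective and the registry display tied to it are not affected. A pooled 10-year rate is possible under the current wording but not certain. Nothing in the documents applies the Synopsis thresholds of 80% and 88% to the pooled curve, and the conclusion does not rely on them. This should be fixed before analysis; it does not threaten the study's main conclusion.

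**What to change.** Choose one of two changes to section 9.1.5:

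1. Delete the pooled curve and any rate from it, in line with section 2.1.2 and the Synopsis. This is a wording change and the safer choice.
2. Keep it, labelled supplementary, with each retrospective knee entering the risk set at its consent date in years since surgery. That curve then needs a procedure that accepts entry times in place of plain PROC LIFETEST.

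Either way, state that the reported 10-year rate and interval, and any registry or 80%/88% comparison, use the prospective-only estimate, and name the interval type. Reconcile the surgery-year wording of section 7.1 with the Evaluation Schedule footnote.

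No new data are needed: the sample forms in Appendix E already record the consent and surgery dates. The cost is a less favourable pooled figure, or none. Delayed entry brings a modest precision gain (SD of the 10-year estimate 0.034 to 0.043, against 0.047 to 0.048 for prospective-only, at true 80%). It does not remove other differences between the cohorts, and it was unbiased here only because both were given the same hazard.

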9.2 Safety

9.2.1 Safety Parameters

Safety parameters include all protocol defined adverse events reported.

9.2.2 Safety Analysis

All adverse events will be listed, tabulated, and summarized by event, number, and percent of cases/patients. Adverse event rates and exact 95% confidence intervals will be presented.

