8.1 Adverse Event (AE) Reporting Requirements for this study

- All adverse events that meet the definition of serious (not to include elective surgeries)
- All AE's related to operative site, regardless of seriousness

See Adverse Event Decision Tree - Figure 1

Adverse Event Reporting Period

The study period during which adverse events must be reported is normally defined as the period from the initiation of any study procedures to the end of the study treatment follow-up. In other words, the start of study procedures is considered to be the point of consent. Therefore, any adverse events which fit the protocol defined reportable events must be reported from the time of obtaining consent throughout the study duration.

At each contact with the subject, the investigator must seek information on adverse events by specific questioning and, as appropriate, by examination. Information on protocol defined adverse events should be recorded immediately in the source document, and also in the appropriate adverse event module of the case report form (CRF). All clearly related signs, symptoms, and abnormal diagnostic procedure results should be recorded in the source document, though they should be grouped under one diagnosis. The clinical course of each event should be followed until resolution or until it is determined at the end of the study that the adverse event will not resolve.

During the medical record review of the retrospectively enrolled cases, any operative site adverse events will be documented as per the usual procedure. For prospective follow-up, these cases will adhere to the adverse event reporting described above.

General Physical Examination Findings

At screening for inclusion into the study, any clinically significant abnormality should be recorded as a preexisting condition. During the study, any new clinically significant findings/abnormalities that meet the definition of a protocol defined adverse event must also be recorded and documented as an adverse event.

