8.2 General Adverse Event Definitions

Following is a list of definitions related to adverse events.

Adverse Event

An *adverse event* (AE) is any untoward medical occurrence in a clinical investigation subject, which changes the medical baseline of the subject. An adverse event can be an unfavorable and unintended sign, symptom or disease, whether or not related to the study device (AEs may also

CONFIDENTIAL

be referred to as complications). In this study only adverse events that are either serious or related to the operative site are to be reported (see Figure 1).

Anticipated Adverse Event

An *anticipated adverse event* is an AE, of which the nature, severity or degree of incidence is known and identified in applicable product labeling, published literature or study protocol. The list of events which are anticipated are provided in the Risk/Benefit Assessment (section #12).

Adverse Device Effect

An *adverse device effect* (ADE) is a negative change in the subject's health that may have been caused by or associated with the use of the device.

Serious Adverse Event

A serious adverse event (SAE) meets one or more of the following definitions:

- Resulted in in-patient hospitalization
- Resulted in prolonged existing hospitalization
- Resulted in persistent or significant disability/incapacity
- Resulted in permanent impairment of a body function or permanent damage to a body structure
- Necessitated medical or surgical intervention to preclude permanent impairment of a body function or permanent damage to a body structure
- Was a life-threatening situation
- Resulted in patient death

Unanticipated Adverse Device Effect

An *unanticipated adverse device effect* (UADE) is any serious adverse effect on health, safety or any life-threatening problem or death caused by, or associated with a device, if that effect, a problem or death not previously identified in nature, severity or degree of incidence, or any other unanticipated serious problem associated with a device and related to the rights, safety or welfare of subjects.

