9.4.4 Safety Patient Population

Safety Population

The safety population will include all non-censored subjects who received the Triathlon® PKR Unicondylar Knee System.

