VI. EVENTS			77 19 -	77.4 6.75	ALVEN !			
M. Have there been any protocol defined Adverse Events since the last visit? Yes* No *If Yes, complete an AE form for each. USE THIS SECTION TO REPORT MEDICAL EVENTS OTHER THAN PROTOCOL DEFINED ADVERSE EVENTS.								
USE THIS SECTION TO REPO	KI WEDICAL EVENTO	JIREK IRANI	RUIUCU	L DEFINED A	ADVERSI	EEVENIS.		
N. Has the patient seen a do	octor for any medical e	vent since the	last visit	?	. 01	No		
O. Has the patient been hos *If Yes, specify (check all tha	it apply)			Ū		O No	otovol 6	2hauldar
☐ Contralateral Knee	☐ Contralateral Hip [_ ipsiiaterai n	пр ЦС	Contralateral	Shoring	ar 🗀 ibaii	aterai 3	Shoulder
☐ Cataract	Other (specify)		_					
*Provide Details								
P. Is anything currently affect *If Yes, specify	P. Is anything currently affecting the patient's function? Yes* No *If Yes, specify							
VII. COMMENTS	NAME OF TAXABLE PARTY.	William No.		The page	MEN'S		15.00	STEERING BE
INVESTIGATOR NAME (PRINT):				/ker Use Onl		FIAL/DATE:		
INVESTIGATOR SIGNATURE:			Stamp	Date Received:		Receipt		
DATE:/						ification		

Stryker	. ®		Triathlon Post-op A		omes Stud uestionnaii				Page 1	of 1
[name]	_			PATIE	NTID:	6 6 Study #	Site #	Subject #	
GENERAL INFOR										
PATIENT INITIA (If there is no middle initi										
OPERATIVE SII (use one form per side)	DE: OR	Right O I	Left (Check C	ne)	VISIT: O 2 Week	6 Week	3 Month Y	O O 1 2 ear Year	O O 5 7 Year Year	O 10 Year
	s not intende d. You shoul e r to answer	d consult your	physician reg Ilowing:	arding app					vities post surg r related questi	
Very Sedentary		2 3	4	5 6	7	8	9 1	0 Extrem	ely Active	
2) Please rate		itiveness.							,	
Noncompetitive	0 1	2 3	4	5 6	7	8	9 .	10 Verv C	ompetitive	
3) Please rate							Marine.	101,0	ompounto	
Unsatisfied	0 1	2 3	4	5 6	7	8	9	10 Extrem	nely Satisfied	
4) Have you con 4a) Please r Low Prior	ate your com	rehabilitation pro nmitment to yo 1 2		Yes nabilitation	program.	* If No, plea		question 4a	Extremely Comm	nitted
O I do not d	currently part y participate	ticipate because and the activi	se I do not like ities are listed s, do not com	e to do red I below. Diete the re	reational or s	sport activ	rities.			orm.
Activity		How many times a WEEK do you do this?	average	ivity on per	Activi	ty	time	w many s a WEEK ou do this?	How long do do this activit average po session?	ty on er
Example:										
Walk		3		mins						mins
				mins						mins
				_ mins						mins
			 	_ mins						mins

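### Pooled crude adverse-event percents include at least 95 retrospective cases that had to be alive and unrevised at entry, so death and AE-table revision will tend to look better than a 10-year rate from surgery

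*Combined protocol and SAP*

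**What the plan says.** - **Population and summary.** Section 9.4.4: "The safety population will include all non-censored subjects who received the" study device, with no split by cohort. Section 9.2.2: "All adverse events will be listed, tabulated, and summarized by event, number, and percent of cases/patients", with exact 95% confidence intervals. Neither section names a time-to-event or delayed-entry method.
- **Size.** Section 3.3 gives 80 prospective cases and a planned minimum of 95 retrospective cases, 175 knees in all.
- **Retrospective entry.** Section 10.1, on patients implanted outside the prospective phase: "it will be determined if they are deceased or had the device revised, which would exclude them during the screening process". Section 7.1 takes the five-year visit as the earliest accepted, so that "subjects will have to have a surgery date of 2015 or earlier".
- **Reporting window.** Section 8.1: "any adverse events which fit the protocol defined reportable events must be reported from the time of obtaining consent throughout the study duration". For the record review of retrospective cases it commits only to this: "any operative site adverse events will be documented as per the usual procedure". Death is a reportable serious event; one of the criteria in section 8.2 is "Resulted in patient death".
- **Use.** Sections 2.2 and 12.3 set these rates against literature rates at 10 years. Table I in 12.3 has revision rows and a death row.
- **Protection elsewhere.** Section 2.1.2 restricts the survival analysis to prospective cases in order to avoid bias, and 9.1.5 displays a prospective-only curve beside a combined one. Section 9.4.1 allows subgroup presentation where appropriate, with centre as its only example.

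**The concern.** A prospective case is at risk of a recorded death or revision from the day of surgery. A retrospective case is not: had either event happened before screening, the case would not be in the study. More than half of the denominator is therefore event-free by selection for its first years, yet each such case counts as a full case in the percent. The result is not a 10-year rate from surgery, although the safety objective reads it as one.

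The plan recognises this kind of bias for survivorship and guards against it there. It states no such guard for the adverse-event tables. For revision the gap is confined to those tables. For death there is no prospective-only analysis anywhere in the plan.

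A lesser, related gap is that serious events away from the operative site and before consent are not clearly collected for retrospective cases, so they may be under-counted.

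**Working it through.** **Plan's own figures.** The safety sections state no expected rate or precision, so there is no safety figure to reproduce. The sample-size paragraph in 9.4.1 does reproduce: (21 × (1.645 + 0.842)/6)² = 75.7, rounded up to 76, and 76/0.80 = 95. Its 20% attrition is used in step 5.

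**Inputs.** 80 and 95 cases (3.3). True 10-year rates of 12% and 20% are illustrative, being the complements of the 88% and 80% success thresholds in the synopsis. A 10% to 25% range for death is my assumption, with one knee per patient, because patient counts are not given.

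**Step 1, entry time E.** Version 2.0 is dated 26-Sep-2019, and retrospective enrolment is estimated at six months (3.4). Under section 7.1 the latest eligible surgery, 31 December 2015, is 3.7 years old at the version date and 4.2 years old six months later; older surgeries enter later. The Evaluation Schedule footnote, however, makes 2015 the earliest surgical year, and 3.3 also admits cases done after the original enrolment goal was met. Both may allow earlier entry. I therefore show E = 2, 4 and 5.

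**Step 2, direction.** With net survival S(t), a retrospective case has event probability q = 1 − S(10)/S(E). Since S(E) ≤ 1, q ≤ p = 1 − S(10). The pooled rate is (80p + 95q)/175, so at equal risk and without attrition it is at or below p.

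**Step 3, size.** With Weibull shape k and H = −ln(1 − p), q = 1 − exp(−H[1 − (E/10)^k]). Example: p = 0.12, k = 1, E = 4 gives H = 0.1278, q = 1 − exp(−0.0767) = 0.0738, and pooled = (80 × 0.12 + 95 × 0.0738)/175 = 0.0949, which is 0.79 of the truth.

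| True rate, hazard | E = 2 | E = 4 | E = 5 |
|---|---|---|---|
| 12%, constant | 10.8% (0.90) | 9.5% (0.79) | 8.8% (0.74) |
| 12%, early-weighted (k = 0.5) | 9.2% (0.77) | 8.0% (0.66) | 7.5% (0.62) |
| 12%, late-weighted (k = 2) | 11.8% (0.98) | 11.0% (0.92) | 10.5% (0.87) |
| 20%, constant | 18.0% (0.90) | 15.9% (0.80) | 14.9% (0.74) |

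For death at constant hazard, a true 10% appears as 7.9% (E = 4) or 7.4% (E = 5), and a true 25% as 20.0% or 18.7%.

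In 2,000 simulated studies with entry spread over years 4 to 5 and a true rate of 12%, the pooled percent averaged 9.2%. The prospective-only percent and the delayed-entry Kaplan-Meier estimate both averaged 12.1%. The pooled exact 95% interval covered the truth in 84% of runs, against 98% for prospective-only; at a true 20% the figures were 70% and 96%.

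**Step 4, competing death.** The plan's percents are crude, and a death removes the chance of a later revision. Take 12% net revision, 25% deaths at constant hazard and E = 4, and compare pooled with true crude revision: 8.5% against 10.5% (0.81) at constant revision hazard, 9.6% against 10.0% (0.96) at k = 2, and 9.9% against 9.7% (1.02) at k = 3. The inequality in step 2 therefore does not carry over to crude revision percents.

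**Step 5, attrition.** With 20% lost at constant hazard and a true 12%, the prospective-only crude percent is 10.8% (0.90) at constant event hazard and 10.4% (0.86) at k = 2. Splitting the table by cohort therefore does not by itself give a 10-year rate.

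**The case against.** The best case for the plan is that little turns on these percents. Revision, the main device outcome, already has a prospective-only curve, and 2.1.2 sets study survivorship beside registry data. No safety hypothesis is tested. Table I is itself heterogeneous: its death rows run from 2% to 84%, with follow-up from 2 to at least 21 years, so a shift from 10% to between 7.4% and 7.9% may not alter a descriptive reading. All events will be listed, and 9.4.1 says follow-up data are generally summarised by visit, which could separate early from late events. This stands as a limit on the consequences. It does not supply a cohort split or a denominator at risk, and it does not help death.

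Equal risk is also an assumption. Under constant hazard, the retrospective hazard would have to be 10/(10 − E) times the prospective one to cancel the shortfall: 1.25, 1.67 or 2.0 at E = 2, 4 or 5. The documents do not point to such an excess. The upper age limit of 75 applies at enrolment (4.1), so retrospective cases at that limit were younger at surgery.

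A reader might infer that every pooled percent must understate the truth, whatever the hazard. Step 4 shows that this fails for crude revision percents. A reader might also infer a definite under-count of serious events before consent. The documents give no capture rate, and the post-operative form asks "Have there been any protocol defined Adverse Events since the last visit", which may pick up some of them, so the extent is unknown.

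**Conclusion.** The concern holds as a bias in descriptive reporting and is worth fixing before the tables are produced. Given equal cohort risk, no attrition and the net scale, the pooled rate cannot exceed the true 10-year rate. For entry at year 4 to 5 it is about 0.62 to 0.92 of a true 12% over Weibull shapes 0.5 to 2. Entry nearer year 2, if the surgery-date passages allow it, brings the constant-hazard figure to about 0.90.

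Death is the outcome most exposed. For revision only the adverse-event table is affected, and with death competing the shortfall there can shrink, vanish or slightly reverse. The documents do not support a claim that the study's revision survivorship as a whole is biased, since the prospective-only curve stands, or that any formal safety conclusion is invalid, since none is planned. The rates used are illustrative, not observed results for this device.

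**What to change.** - In 9.2.2, present adverse-event numbers, percents and exact intervals by cohort.
- For death and revision, base the 10-year literature comparison on time-to-event estimates from surgery in the prospective cohort: Kaplan-Meier for death, Kaplan-Meier or cumulative incidence for revision. Alternatively, use a delayed-entry (left-truncated) estimate from both cohorts. Do not use pooled crude percents for this comparison.
- Report retrospective serious events away from the operative site from consent onward only.
- Reconcile the surgery-date wording in the Evaluation Schedule footnote, 3.3 and 7.1, so that entry time is defined.

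The cost is plan wording, extra tables and wider intervals where 80 cases carry the comparison: for example, 6/80 = 7.5% (exact 95% interval 2.8% to 15.6%) against a pooled 9/175 = 5.1% (2.4% to 9.5%). Delayed entry recovers part of the precision. In the 12% simulation its standard deviation was 2.95 percentage points, against 3.57 for prospective-only.
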